
[name] [name] Assistant [name] of Biostatistics and Epidemiology School of Public Health and Health Sciences University of Massachusetts – Amherst [contact]
	
[name] Independent consultant [contact]
	
[name] Assistant [name] School of Public Health and Tropical Medicine [contact]

[name], MA Assistant [name] of Medicine / Div. of Infectious Diseases University of California, San Francisco [contact]
		

1 Protocol summary

Aim	To determine the effectiveness and feasibility of enhanced reactive case detection (RACD) targeting high-risk villages and forest workers for reducing Plasmodium falciparum and Plasmodium vivax transmission in southern Lao PDR
Primary research question and hypothesis	
1. Null hypothesis: Compared to standard of care, which includes case management and RACD with conventional RDTs and is directed at villagers, there is no additional benefit of enhanced community-based RACD, which is conducted by village malaria workers (VMWs), uses HS-RDTs, and targets forest workers in addition to villagers, for reducing P. falciparum and P. vivax confirmed case incidence and parasite prevalence over an 18-month period in Lao PDR.
 
Research hypothesis: Enhanced community-based RACD will be more effective than standard of care case management and RACD at reducing P. falciparum and P. vivax confirmed case incidence and parasite prevalence over an 18-month period in Lao PDR.

Research objectives	
Primary Objective: To evaluate the effectiveness of reactive case detection (RACD) using HS-RDTs, targeting both village and forest working populations, compared to control for reducing the health center catchment-level incidence and prevalence of P. falciparum and P. vivax within two provinces in Lao PDR.
 
Secondary Objectives:
 
 1. To determine the operational feasibility, cost-effectiveness, and acceptability of targeting high-risk populations with community-based reactive case detection strategies aimed at reducing P. falciparum and P. vivax transmission among village and forest working populations. 2. To determine the operational feasibility and safety of conducting G6PD testing and PQ administration and follow-up at the community level. 3. To determine factors associated with G6PD testing after referral to district or provincial-level facilities for persons with P. vivax positive RDT results, and subsequent adherence to Primaquine treatment. 4. To assess malaria vector species composition and bionomics in both village and forest settings
Study site and target populations	Total population of approximately 120,000 in 32 health center catchment areas of two Provinces in Lao PDR (Champasak and Saravan Province)
Study design	A cluster randomized controlled trial design will be used to evaluate the enhanced RACD intervention against standard of care
Primary outcome measures for assessing impact	
 1. Cumulative incidence over the study period at the health facility level 2. Prevalence of infection (P. falciparum and/or P. vivax) using qPCR 3. HS-RDT and RDT test positivity rate for RACD
Data collection and sampling period	18 months from start date (June 2019 – November 2020)

Sample size	32 health center catchment areas in Lao PDR
Estimated enrollment	
 1) Confirmed case incidence across 32 health center catchment areas: population of approximately 145,000 2) Village-based reactive case detection: estimated 14,400 3) Forest worker reactive case detection: estimated 2,880 4) Endline household survey: 14,080 persons at end-line 5) Qualitative surveys: 6 Focus group discussions (FGDs) and 18 Key informant interviews (KIIs) at baseline, 9 FGDs and 18 KIIs at end-line. 6) Competency checklists with 32 VMWs at baseline, midline, and endline 7) Entomological human landing catches: 20 collectors over three nights at baseline
Statistical and analytical plan	Rapid reporting of microscopy or RDT and HS-RDT positivity will be analyzed as interventions are implemented (or shortly thereafter) to provide preliminary assessment of interventions. Negative binomial (for incidence) and generalized linear mixed effects (for prevalence) models will be used to test the effect of each intervention independently (main effects) relative to control (standard of care). For the enhanced RACD vs. control comparison, both country-specific and pooled analyses will be conducted.

2 Background and introduction

A standard and widely practiced method to identify infections at the community level is reactive case detection (RACD), whereby household and community members of a passively identified index case are tested with either an RDT or by microscopy¹⁻³. However, traditional household-based RACD methods using current diagnostics have shown limited effectiveness for identifying additional infections, especially in settings of forest malaria transmission such as the GMS. Results from a recently conducted UCSF-MEI study of RACD in two Thailand border areas (Chanthaburi and Kanchanaburi Provinces) identified only 0.2% parasite prevalence by PCR in household and community members tested residing around passively identified index cases (n=27); all additional secondary infections identified were *P. vivax* (n=4). Furthermore, a higher risk of malaria infection was associated with being male, aged 31 years and older, and having worked in or near the forest fringe. While there have been several published small-scale observational studies examining the yield of household-based RACD using conventional RDTs in the GMS⁴, none have examined its impact on transmission. Recent pilot studies in Cambodia suggest targeting high risk groups (using PCR) will substantially increase the infections found and cleared⁵. Preliminary results of an observational study of RACD targeted to high-risk forest workers (using LAMP) in Aceh Province, Indonesia carried out by UCSF-MEI suggest that substantially more secondary infections will be identified when RACD is targeted to high-risk groups compared to standard RACD in the neighborhood of cases. None of these studies have used the newly available HS-RDTs for *P. falciparum*⁶; evidence suggests these will increase the sensitivity of active case detection over standard RDTs and have greater utility for community-based approaches where PCR or LAMP are not likely to be feasible, but rigorous testing is needed in routine operational settings, especially in *P. vivax* co-endemic settings.

Recent results from an observational trial in Myanmar demonstrate the effectiveness of early diagnosis and treatment through village-based malaria posts and mass drug administration for *P. falciparum* in hotspot villages⁷. In 2018, the UCSF-MEI conducted a community randomized control trial of mass test and treat (MTAT) in villages combined with focal test and treat (FTAT) in forest workers led by forest-working peer navigators using HS-RDTs in Champasak, Lao PDR, which helped inform community-based approaches for targeting RACD to high-risk forest workers in this proposal. Additionally, the UCSF-MEI is conducting formative ethnographic and epidemiological research to understand forest worker and other high-risk populations in several provinces in southern Lao PDR, working closely with Health Poverty Action (HPA) within their Malaria Post/village malaria worker (VMW) networks. These studies have highlighted the importance of involving the community, especially high-risk individuals, as part of community-based active surveillance and response strategies, and further operational research is essential to assess feasibility and challenges associated with scaling up such community-based approaches.

Safe and effective management of *P. vivax* cases requires addressing glucose-6-phosphate dehydrogenase (G6PD) deficiency and ensuring patients with G6PD normal function complete a 14-day treatment regimen with primaquine. The heterogeneity and severity of G6PD deficiencies in SE Asia and associated risk of severe hemolysis with oxidative drugs such as primaquine is an especially serious public health issue⁸. The majority of *P. vivax* cases in most transmission settings are due to relapses⁹, making primaquine (and tafenoquine when available) a critical component of elimination activities. However, treatment adherence for full 14-day primaquine is generally sub-optimal, and standard of care use of primaquine in health systems has shown minimal effectiveness in preventing relapses¹⁰. There are limited data on primaquine use in Lao PDR; a study conducted by WHO and CMPE in 2015 enrolled 1,577 *P. vivax* cases (363 women) for G6PD testing of which 67 (4.2%; 95% CI: 3.3 to 5.3%) were classified as deficient.¹¹ A total of 1,225 G6PD non-deficient individuals with *P. vivax* infection were enrolled for PQ administration, of which 889 (72.5%) completed follow-up hematocrit testing, and only one individual experienced a serious drop in hematocrit (below 25%). However, treatment adherence and parasite clearance were not measured in the study. This study and others

suggest that there remain key gaps in knowledge to inform safe and effective programmatic use of primaquine drug regimens to target the hypnozoite reservoir, especially with regards to ensuring adequate follow-up and safety monitoring at all levels of the health system including the community level.

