All individuals who test positive by either HS-RDT or Standard RDT will be told of their results and treated on site per national guidelines:

- Individuals with *P. falciparum* infection will be treated with an age-appropriate course of artemether-lumefantrine (AL) and a single low dose of primaquine (SLD-PQ). Weight-based dosing is described in Tables 2 and 3 below.
- At all study sites in Lao PDR, patients with a *P. vivax* infection identified by RDT (both febrile and asymptomatic) will be given a unique coded and signed informational letter directing them to the nearest district hospital (or other testing facility) for G6PD deficiency testing and possible radical cure administration depending on results. Study contact information will also be included if the participants present at other health facilities. At the health facility, G6PD normal individuals will be treated with AL and a 14-day course of PQ, whereas G6PD deficient individuals will receive AL alone as per the national guidelines and referred to a hospital for further primaquine management decisions. The study staff will meet with district hospital and health facility staff monthly from all study areas and nearby district hospitals and health facilities to collect these forms, with small incentives for health staff to report receiving a study card (phone top up card, etc.) to maximize data completeness. After six months of implementation, a subset of VMWs will begin conducting qualitative G6PD testing and treatment administration at the community-level with the assistance of a health facility staff member.

Table 2. AL weight-based dosing

Body weight (kg)	Tablet strength (mg)		Tablets/dose	Mg of drug per dose		Tablets/day
	Artemether	Lumefantrine		Artemether	Lumefantrine	
5 to 14	20	120	1	20	120	1 tablet given twice* per day for 3 consecutive days

15 to 24	20	120	2	40	240	2 tablets given twice* per day for 3 consecutive days
25 to 34	20	120	3	60	360	3 tablets given twice* per day for 3 consecutive days
35 or greater	20	120	4	80	480	4 tablets given twice* per day for 3 consecutive days
*Approx. 8 hours between doses 1 and 2. Approx. 12 hours between all other consecutive doses.						

Table 3. Weight-based dosing of SLD- Primaquine (.25 mg/kg) for *P. falciparum*

Body weight (kg)	SLD-PQ dose (7.5 mg tablet) (as base)	Tablets
10 to < 25	3.75	1/2
25 to < 50	7.5	1
50 to 100	15	2
*Given as SLD in addition to AL for P falciparum positive		

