Activity 3: Assessment of the operational feasibility and safety of conducting G6PD testing, referral, and treatment adherence among positive P. vivax RDT cases	1. Assess the operational feasibility of G6PD referral at community level	Proportion of VMWs who rate conducting G6PD referral as very easy, somewhat easy, somewhat difficult, and very difficult, and changes in proportions over time	Entrance, mid-intervention, and exit competency checklists with VMWs; focus group discussion and interviews with VMWs at end-line	
		Proportion of P. vivax cases with valid recorded G6PD result	VMW and health facility records	
	2. Determine risk factors for non-attendance at hospitals or health centers after referral for G6PD testing	Proportion of referred cases presenting at hospitals or health centers for G6PD testing.	Cross-sectional survey and qualitative studies at endline with villagers, forest workers, VMWs	
	3. Assess treatment adherence among positive P. vivax RDT cases	Proportion of patients with physical evidence of full adherence with the prescribed drug regimen	VMW follow-up visits on day 3, 7, and 14	
		Proportion of P. vivax cases who relapsed in the six months following treatment	VMW and health facility records	
	4. Assess the safety of community-level G6PD testing, referral, and P. vivax treatment follow-up	Adverse event rate per treated individual	RACD intervention data and VMW follow-up visits; health facility adverse event reporting forms	
	Activity 4: Assessment of the risk of malaria vector biting in forest and village settings	1. Describe local vector species composition and bionomics in forest and village settings	Vector occurrence and density by species; vector biting behaviors; human behavioral observations in relation to human biting rate (HBR)	Human Landing Catches (HLCs) vector sampling at baseline

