3.4.3.2. Primary outcomes measures

1. Population coverage of enhanced RACD interventions: this indicator will be measured in two ways. Operational program coverage will be defined as the proportion of individuals ≥ 18 months old and households visited and offered the RACD interventions within the target areas per time period. Effective program coverage is defined as the proportion of individuals (≥ 18 months old) that agreed to participate in the RACD intervention among all individuals ≥ 18 months old eligible to participate in the intervention in the target population per time period.
2. Feasibility of conducting enhanced RACD intervention at the community level: feasibility will be determined based upon a combination of population coverage data, responses of provincial, district, and health staff, VMWs, and community members to KIIs and FGDs at baseline and endline, VMW competency checklists at baseline, midline, and endline, and cost data.
3. Acceptability of community-based RACD approaches: acceptability will be determined based upon refusal rates during interventions and responses of community members and VMWs to endline questionnaire, interviews, and focus groups.
4. Safety of community-based RACD and treatment follow-up: safety measures will include the adverse event rate amongst treated individuals and hemoglobin measurement pre and post treatment for individuals receiving PQ.
5. Operational feasibility of G6PD referral: operational feasibility of G6PD referral will be determined by the results of the process-mapping and co-design workshops at baseline, responses of health staff and VMWs to interviews and focus groups at baseline and endline and competency checklists at baseline, midline, and endline, the proportion of referred *P. vivax* cases presenting at a health facility for G6PD testing, and the proportion of *P. vivax* cases with a valid recorded G6PD result.
6. Assessment of *P. vivax* treatment adherence: treatment adherence will be determined by the proportion of *P. vivax* cases with physical evidence of adherence through pill count, the *P. vivax* relapse rate across study arms, and the proportion of *P. vivax* cases with successful parasite clearance on day 14.

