The adverse event rate for RDT positive participants will be assessed using intervention data and health facility adverse event reporting forms. Study staff and VMWs will be trained on detection of adverse events for positive cases receiving treatment.

Outcome 5: Operational feasibility of G6PD referral, testing and non-adherence

The operational feasibility of G6PD referral, testing and non-adherence at the community and facility levels will be evaluated. For testing, interview data at baseline and endline will be collected from district health staff and community members, as well as focus group discussions with both groups at end-line. Risk factors for non-adherence to G6PD testing after referral will be determined through comparison of factors captured at enrollment for individuals who were tested at a facility versus those who were not.

Outcome 6: Assessment of *P. vivax* treatment adherence

The treatment adherence of *P. vivax* positive study participants will be assessed through physical evidence of adherence during VMW follow-up visits on day 3, 7 and 14 and comparison of relapse rates across study arms.

3.4.4. Assessment of the risk of malaria vector biting in forest and village settings

A baseline entomological investigation will be conducted along with the baseline qualitative activities in Aug/Sep 2019. The investigation will involve collection of vector occurrence and density data (by species), human landing catches (HLC) to assess vector biting behaviors (indoor vs outdoor and forest sites), and household structure type, and human behavioral observations. All collections will take place over a one-week period. HLC collections will occur in 4-5 sleeping structures each in the forest and village, with 2 HLC collectors by structure. At the end of each HLC collection hour, collectors will also record human behavior (sleeping (or awake) under net/sleeping without net/awake), both indoors and outdoors. Field collectors will be community volunteers that will have been properly informed about the sampling methods and their implications, and who have consented to participating by signing consent forms. Prior to the start of collections, volunteers will also need to be tested for malaria. Depending on national policy, they may also be required to take malaria prophylaxis. HLC data collection forms are found in the Appendix.

4 Ethical issues related to human subjects research

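### The safety analysis pools adverse events over all RDT-positive participants, so it cannot show whether community-level G6PD testing with 14-day primaquine was safe

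*Protocol*

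**What the plan says.** The objective (Protocol summary, Research objectives, Secondary Objective 2) is "To determine the operational feasibility and safety of conducting G6PD testing and PQ administration and follow-up at the community level".

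Three places define its safety measure:

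- Section 3.4.1, Table 4 (Overview of evaluation activities), Activity 3, objective 4: "Adverse event rate per treated individual". The activity is headed as concerning P. vivax RDT-positive cases.
- Section 3.4.3.2, item 4: "safety measures will include the adverse event rate amongst treated individuals and hemoglobin measurement pre and post treatment for individuals receiving PQ".
- Section 3.4.3.5, Outcome 4: "The adverse event rate for RDT positive participants will be assessed using intervention data and health facility adverse event reporting forms".

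Section 3.3.1 (Case Management and Follow-up) describes several treatment routes:

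- P. falciparum patients get artemether-lumefantrine (AL) plus single low-dose PQ on site.
- P. vivax patients are referred to a facility for G6PD testing. Those with a normal result get AL plus 14-day PQ; those who are deficient get AL alone.
- After six months, "a subset of VMWs will begin conducting qualitative G6PD testing and treatment administration at the community-level". Neither this section nor 4.2 gives the size of that subset.

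**The concern.** Section 4.2 names acute hemolytic anemia after PQ in G6PD-deficient people as the main safety concern, and section 5.1 acknowledges that a deficient person may be misclassified and given 14 days of PQ. Testing and treatment by VMWs is the new setting for that risk. In the analysis text, people exposed in this way share a numerator and denominator with patients on single low-dose PQ, patients on AL alone and patients tested at a facility. A reader given one rate cannot recover the rate in the VMW-tested group, so a reassuring pooled figure could be cited for community-level 14-day PQ when it mostly describes other people.

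**Working it through.** **1. The plan's own figures.**

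- People tested in reactive case detection (RACD), section 3.4.2.4.3: 720 × (5 × 4 + 4) = 17,280, as stated.
- Table 1 in section 3.1: the population-weighted district rates give about 588 P. falciparum and 413 P. vivax cases in 147,798 people, or 3.98, 2.79 and 6.77 per 1,000, as stated. The P. vivax share is 2.79 / 6.77 = 41.2%.

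**2. Share of treated people given 14-day PQ after VMW testing.** Let f be the fraction of P. vivax cases in months 7 to 18 handled by the VMW subset. The protocol does not give f. Further assumptions are that those treated have the Table 1 species mix and that cases are spread evenly over 18 months. Then s = 0.412 × (12/18) × f. If this group's adverse event rate is five times that of everyone else, the pooled rate is multiplied by (1 − s) + 5s = 1 + 4s.

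| f | s | pooled rate multiplied by |
|---|---|---|
| 10% | 2.7% | 1.11 |
| 25% | 6.9% | 1.27 |
| 50% | 13.7% | 1.55 |
| 75% | 20.6% | 1.82 |
| 100% | 27.5% | 2.10 |

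Even at f = 100%, 72.5% of the denominator lacks the exposure. Removing the 4.2% classified as G6PD deficient in the study described in section 2 changes 6.9% and 13.7% to 6.6% and 13.2%.

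**3. If the Table 4 denominator means P. vivax cases only.** The share is (12/18) × f: 16.7% at f = 25%, 33.3% at 50% and 66.7% at 100%. The multiplier at 25% and 50% is 1.67 and 2.33. There is less dilution, but facility-tested and VMW-tested patients are still mixed.

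**4. Detectability, as an illustration.** Assume 2.5% RDT positivity, so 17,280 × 0.025 = 432 treated, and a 2% background adverse event rate. Without excess risk, 432 × 0.02 = 8.6 events are expected. With the fivefold rate the total is 11.0 (f = 25%) or 13.4 (f = 50%), a pooled rate of 2.5% or 3.1%. Normal-approximation power, two-sided 5%:

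- Pooled rate against a known 2% reference: 0.15 or 0.40. This is generous, because the analysis text names no reference.
- VMW-tested group (about 30 or 59 people) against the rest: 0.65 or 0.79.

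With positivity of 0.2% to 2.5%, background rates of 1% to 5%, the 720 index cases in or out, and f of 25% or 50%, pooled power runs from 0.06 to 0.97 and separate power from 0.22 to 1.00. The approximation is rough where counts are very small.

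**5. The hemoglobin measure.** It is defined in 3.4.3.2, item 4. It does not appear in Table 4 or in 3.4.3.5. In 3.3.1 the RACD finger-prick sample goes to the two RDTs and the filter paper. In 3.3.2 the follow-up visits consist of questions and tablet counts. A Hemocue test is described only for the endline survey (3.4.2.5.2), which is not tied to treatment. As worded, the measure also covers single low-dose and 14-day PQ together, wherever given.

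**The case against.** The strongest reply is that the adverse event rate is not the only safeguard. There is the hemoglobin measure. There are visits on days 3, 7 and 14 for everyone on PQ for P. vivax, PROMPT tracking of PQ recipients, questions about hemolysis, causality grading of each serious event (3.3.2), and G6PD genotyping where an event suggests hemolysis (3.4.2.7). This stands against any inference that harm in the VMW-tested group would go unnoticed: individual serious events would be reviewed. It does not supply a rate for that group, and the hemoglobin measure is not carried into the analysis or the described procedures.

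Second, Activity 3 concerns P. vivax cases, so its denominator may exclude P. falciparum patients. That is a fair reading of Table 4, but it conflicts with Outcome 4, and step 3 shows that it does not isolate the community-level group either.

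Third, the objective does not say 14-day PQ only. Single-dose PQ given on site and VMW follow-up of facility-treated patients fall partly within it. This stands, and the fix allows for it.

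Fourth, a statistical analysis plan, not shown here, could split the rate. It could, but the point rests on the denominators the protocol itself states, which disagree.

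Two stronger readings are tempting. One is that a fivefold excess would hardly be visible. A rise of 27% to 55% is not negligible, and pooled power reaches 0.97 with about 1,150 treated, a 5% background rate and f = 50%. The other is that feasibility is unmeasured because the VMW ease rating asks about referral. The protocol also records the proportion of P. vivax cases with a valid G6PD result, evaluates testing under Outcome 5 of 3.4.3.5, and covers testing and primaquine in interviews and focus groups.

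**Conclusion.** The point holds as a mismatch between objective and analysis. Followed as written, Outcome 4 yields a rate in which the VMW-tested 14-day PQ group is a minority of unstated size: 2.7% to 27.5% for f from 10% to 100%. No figure within that range is the protocol's own. All of them depend on the unstated f and on applying the Table 1 mix to those treated. The district P. vivax share runs from 9% to 95%, and the HS-RDT detects only P. falciparum, so the mix in RACD may differ. The qualitative conclusion does not depend on f: under either reading of the denominator, the pooled rate does not separate VMW-tested from facility-tested patients. The three denominators disagree, and one named safety measure has no analysis and no described collection. Nothing here shows that community-level PQ is unsafe.

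**What to change.** 1. Reconcile the denominators in Table 4 (Activity 3, objective 4), 3.4.3.2 item 4 and 3.4.3.5 Outcome 4.
2. Report the adverse event rate with exact confidence intervals separately for AL plus single low-dose PQ, 14-day PQ after facility testing, and 14-day PQ after VMW testing. Name the last as the main evidence on community-level G6PD testing with 14-day PQ. Single-dose PQ given on site and VMW follow-up of facility-treated patients inform the rest of the objective.
3. Reconcile the hemoglobin measure with the analysis and procedure text and, if it is collected, report it by the same groups.
4. Confirm that the data forms record regimen and tester. Only their titles are listed in the appendices, so this cannot be checked here.

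The cost is mainly wording, provided the forms hold those two items. The drawback is precision. With no events, the exact 95% upper limit is 1 − 0.025^(1/30) = 11.6% for 30 people and 1 − 0.025^(1/59) = 6.1% for 59. That width should be shown, because it is what the trial can say about this group. Adding G6PD testing and PQ administration to the VMW ease rating is optional.
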